6.1.2. AEs and SAEs

6.1.2.1. Main Analysis

- Estimand strategy: Treatment policy (Section 2.2.1).
- Analysis set: Safety population (Section 4).

- Analysis methodology: 95% CI of the proportion of participants reporting those events, using the Clopper-Pearson method (Section 5.2.1).
- Analysis timing: Day 1 through 4 weeks after vaccination for AEs; Day 1 through 6 months after vaccination for SAEs.
- Intercurrent events and missing data: All data collected are included. Missing AE dates will be imputed as described in Pfizer's Vaccine Statistics Rulebook.
- Reporting results:
 - The number of participants with AEs though 4 weeks after vaccination (n), proportion (%), and associated 2-sided Clopper-Pearson 95% CI will be presented for each study intervention group and overall, for participants 18 through 64 years of age and ≥65 years of age separately and combined.
 - The number of participants with SAEs though 6 months after vaccination (n), proportion (%), and associated 2-sided Clopper-Pearson 95% CI will be presented for each study intervention group and overall, for participants 18 through 64 years of age and ≥65 years of age separately and combined.
 - O Descriptive statistics, including the proportion (%), the numerator (n) and the denominator used in the proportion calculation, and the 95% CI for percentage using the Clopper-Pearson method, will be presented for each SOC and each PT within each SOC for each study intervention group and overall, for participants 18 through 64 years of age and ≥65 years of age separately and combined.

6.1.2.2. Sensitivity/Supplementary Analysis

To support the assessment of AEs, the endpoints below as specified in Section 3.1.4 and Section 3.1.5 will be summarized with the same analysis population using the same presentation as specified in the main analysis:

- Immediate AEs
- Related AEs
- Severe AEs
- Life-threatening AEs
- AEs leading to study withdrawal
- AEs leading to death
- AESIs

All AEs/SAEs after informed consent signing and prior to vaccination will not be included in the analyses but will be listed.

In addition, any AEs occurring up to 48 hours after blood draws at Visit 4 and Visit 5 will be listed.

6.1.3. Laboratory Parameters

6.1.3.1. Main Analysis

- Estimand strategy: Treatment policy (Section 2.2.1).
- Analysis set: Safety population (Section 4).
- Analysis methodology: Descriptive summary statistics (Section 5.2.1).
- Analysis timing: Within 2 to 4 and within 6 to 8 days after vaccination.
- Intercurrent events and missing data: All data collected are included. Missing dates/laboratory values will be imputed as described in Pfizer's Vaccine Statistics Rulebook.
- Reporting results: The number of participants with abnormal troponin I laboratory values within the visit window at Visits 2 and 3 after vaccination (n), proportion, and associated 2-sided Clopper-Pearson 95% CI will be presented by study intervention group, for participants 18 through 64 years of age and ≥65 years of age separately and combined.

6.1.4. Electrocardiograms

6.1.4.1. Main Analysis

- Estimand strategy: Treatment policy (Section 2.2.1).
- Analysis set: Safety population (Section 4).
- Analysis timing: Up to Visits 2 and 3 after vaccination.
- Analysis methodology: Descriptive summary statistics (Section 5.2.1).
- Supporting objective: Primary safety objective.
- Intercurrent events and missing data: All data collected are included. Missing ECG values will be handled according to Pfizer safety rules.
- Reporting results: The number of participants with new ECG abnormalities up to Visits 2
 and 3 after vaccination (n), proportion, and associated 2-sided Clopper-Pearson 95% CI
 will be presented for each study intervention group, for participants 18 through 64 years
 of age and ≥65 years of age separately and combined.

6.2. Secondary Endpoints

6.2.1. Immunogenicity Endpoints

6.2.1.1. Main Analysis

- Estimand strategy: Hypothetical approach (Section 2.2.2).
- Analysis set: Evaluable immunogenicity population (Section 4).
- Analysis methodology: Descriptive summary statistics (Section 5.2.2).
- Analysis timing: 1, 4, and 8 Weeks after study intervention administration.
- Intercurrent events and missing data: All data collected after or at intercurrent events will be excluded. Antibody titers below the LLOQ will be treated as specified in Section 5.3.2. Missing data will not be imputed.
- Reporting results:
 - The SARS-CoV-2 GMT at each time point and GMFRs from before vaccination to
 each time point after vaccination, and the proportion of participants with seroresponse
 at 1, 4, and 8 weeks after vaccination, will be estimated for each strain, by study
 intervention group with a BNT162b2 dose, and separately by age group.
 - Descriptive statistics, including the sample size (n), GMTs, GMFRs, and 95% CI for the GMTs and GMFRs, will be presented for each strain by study intervention group with qIRV (Section 5.2.2), for participants 18 through 64 years of age and ≥65 years of age separately.
 - The proportion of participants achieving HAI seroconversion and the associated 2-sided Clopper-Pearson 95% CIs will be provided for each strain by study intervention group with qIRV, for participants 18 through 64 years of age and ≥65 years of age separately.
 - o The proportion of participants with HAI titers ≥1:40 before vaccination and at each time point after vaccination and the associated 2-sided Clopper-Pearson 95% CIs will be provided for each strain by study intervention group with qIRV, for participants 18 through 64 years of age and ≥65 years of age separately.
 - HAI GMTs for each strain and the associated 95% CIs will be plotted by study intervention group with qIRV, for participants 18 through 64 years of age and ≥65 years of age separately.
 - HAI seroconversion rate for each strain, along with the associated 95% CIs, will be presented by study intervention group with qIRV, for participants 18 through 64 years of age and ≥65 years of age separately.

- SARS-CoV-2 GMT at each time point and GMFRs from before vaccination to each time point after vaccination, and the proportion of participants with seroresponse at 1, 4, and 8 weeks after vaccination, will be provided for each strain by study intervention group with a BNT162b2 dose, and separately by age group.
- SARS-CoV-2 GMTs for each strain and the associated 95% CIs will be plotted by study intervention group with a BNT162b2 dose, for participants 18 through 64 years of age and ≥65 years of age separately.
- o SARS-CoV-2 seroresponse rate for each strain, along with the associated 95% CIs, will be presented by study intervention group with a BNT162b2 dose, for participants 18 through 64 years of age and ≥65 years of age separately.
- Empirical RCDCs with HAI titers and SARS-CoV-2 neutralizing titers will be plotted separately for each strain by study intervention group, for participants 18 through 64 years of age and ≥65 years of age separately.
- Bar charts with the numbers, proportions of participants achieving HAI
 seroconversion, and associated 95% CIs at 4 weeks after study intervention
 administration will be provided for each strain by study intervention group with qIRV,
 for participants 18 through 64 years of age and ≥65 years of age separately.
- Bar charts with the numbers, SARS-CoV-2 seroresponse rate, and associated 95% CI at 4 weeks after study intervention administration will be provided for each strain by study intervention group with a BNT162b2 dose, for participants 18 through 64 years of age and ≥65 years of age separately.

6.2.1.2. Sensitivity/Supplementary Analysis

To support the assessment of immunogenicity, estimands as specified in Section 2.2.2 using the treatment policy strategy may be summarized with the mITT population using the same presentation as specified in the main analysis.

6.3. Other/Exploratory Endpoints

6.3.1. Immunogenicity for Emerging VOCs

6.3.1.1. Main Analysis

- Estimand strategy: Hypothetical approach (Section 2.2.3).
- Analysis set: Evaluable immunogenicity population (Section 4).
- Analysis methodology: Descriptive summary statistics (Section 5.2.2).
- Analysis timing: 1, 2, and 4 Weeks after study intervention administration.
- Intercurrent events and missing data: All data collected after or at intercurrent events will not be included; missing data will not be imputed.

Reporting results:

- SARS-CoV-2 VOC GMTs and associated 95% CIs will be provided for VOCs not already specified, by study intervention group with a BNT162b2 dose, for participants 18 through 64 years of age and ≥65 years of age separately.
- SARS-CoV-2 VOC GMFRs from before vaccination to each time point after vaccination and associated 95% CIs will be provided for VOCs not already specified, by study intervention group with a BNT162b2 dose, for participants 18 through 64 years of age and ≥65 years of age separately.

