10.11.4. Substudy A Design

10.11.4.1. Overall Design for Substudy A

This is a Phase 1 randomized, open-label substudy to describe the safety and immunogenicity of up to 3 dose-level combinations of qIRV/bivalent BNT162b2 (original/Omi BA.4/BA.5). Bivalent BNT162b2 (original/Omi BA.4/BA.5) used was recommended by ACIP in 2022-2023. Approximately 360 participants will be enrolled across 2 age strata: approximately 180 participants 18 through 64 years of age and approximately 180 participants ≥65 years of age. Participants in each stratum will be randomized equally (30 participants per group) to each group to receive a dose of either:

- qIRV/bivalent BNT162b2 (original*/Omi BA.4/BA.5), at 1 of the 3 dose-level combinations shown in Table 1,
- CCI μg qIRV,
- μg qIRV, or
- µg Bivalent BNT162b2 (original/Omi BA.4/BA.5) administered concurrently in the opposite arm to licensed QIV.
- * Original refers to the ancestral strain (Wuhan-Hu-1; USA-WA1/2020), also referred to in this protocol as the reference strain.

Enrollment into each of the 2 age strata (18 through 64 and ≥65 years of age) may occur independently.

Safety and immunogenicity data from studies previously conducted in participants of a similar age range having received 1 dose of BNT162b2 at a dose level of µg and µg may be used as a control during the substudy analysis.

Enrollment in each age stratum will be controlled such that no more than 10 participants (considered the sentinel participants) can be vaccinated on the first day, vaccination of the remaining participants will commence no sooner than 24 hours after the tenth participant received his or her vaccination.

Stopping rules will apply to groups receiving combination bivalent BNT162b2 (original/Omi BA.4/BA.5) and qIRV as detailed in Section 10.11.8.6.

All participants will be asked to complete a reactogenicity e-diary for 7 days following each vaccination. Blood samples of approximately 50 mL will be collected for immunogenicity assessments prior to Vaccination 1 and at 1, 4, and 8 weeks after vaccination. All participants will be asked to provide an additional blood sample of approximately 2.5 mL at time points specified in Section 10.11.1 for assessment of troponin I.

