10.11.8.1. Immunogenicity Assessments for Substudy A

Samples will be collected at time points as specified in Section 10.11.1 from all participants, and the following assays run:

- HAI titers for the matched seasonal strains (CCI) recommended by WHO
- SARS-CoV-2 neutralization assay (reference strain)
- SARS-CoV-2 neutralization assays (Omicron BA.4, Omicron BA.5; other VOCs of interest, including other Omicron sublineages, may also be evaluated)

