- Explain the e-diary completion requirement to the participant and assist the participant
 with downloading the study application onto the participant's own device or issue a
 provisioned device if required. Provide instructions on e-diary completion and ask the
 participant to complete the reactogenicity e-diary from Day 1 through Day 7, with Day 1
 being the day of vaccination.
- Ask the participant to contact the site staff or investigator immediately if he or she
 experiences any of the following from Day 1 through Day 7 after vaccination
 (where Day 1 is the day of vaccination) to determine if an unscheduled reactogenicity
 visit is required:
 - Fever ≥39.0°C (≥102.1°F).
 - Redness or swelling at the injection site measuring greater than 10 cm (>20 measuring device units).
 - Severe pain at the injection site.
 - Any severe systemic event.
- Record AEs as described in Section 8.4.1.
- Ask the participant to contact the site staff or investigator if a medically attended event (eg, doctor's visit, emergency room visit) or hospitalization occurs.
- Ask the participant to contact the site staff or investigator immediately if the participant experiences acute chest pain, shortness of breath, or palpitations (see Section 10.11.8.8.10).
- Schedule an appointment for the participant to return for the next study visit.
- Remind the participant to bring the e-diary to the next visit.
- Complete the source documents.
- The investigator or an authorized designee completes the CRFs and updates the study intervention accountability records.
- The investigator or appropriately qualified designee reviews the reactogenicity
 e-diary data online following vaccination to evaluate participant compliance and as part
 of the ongoing safety review. Daily review is optimal during the active diary period.

10.11.8.8.3. Visit 2 – Day 3 Follow-Up Visit (After Vaccination) – 2 to 4 Days After Visit 1 for Substudy A

- Record AEs as described in Section 8.4.1.
- Record nonstudy vaccinations as described in Section 10.11.6.7.
- Record prohibited medication use as described in Section 10.11.6.7.1.
- Verify understanding of and compliance with protocol requirements for contraception as described in Section 5.3.1.
- Review laboratory results (troponin I) and ECG results. Any abnormal troponin I level
 must result in further assessments as outlined in Section 10.11.8.8.10.

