- Perform 12-lead triplicate ECG. Any new ECG abnormality (compared to baseline) consistent with probable or possible myocarditis or pericarditis (as listed in Section 10.11.8.4.1) must result in further assessments as outlined in Section 10.11.8.8.10.
- Measure vital signs, including oral temperature, pulse rate, and seated blood pressure.
- Collect a blood sample of approximately 2.5 mL as detailed in the laboratory manual for troponin I laboratory testing as described in Section 8.3.4.
- Remind the participant to contact the site staff or investigator immediately if he or she
 experiences any of the following from Day 1 through Day 7 after vaccination
 (where Day 1 is the day of vaccination) to determine if an unscheduled reactogenicity
 visit is required:
 - Fever ≥39.0°C (≥102.1°F).
 - Redness or swelling at the injection site measuring greater than 10 cm (>20 measuring device units).
 - Severe pain at the injection site.
 - Any severe systemic event.
- Remind the participant to contact the site staff or investigator if a medically attended event (eg, doctor's visit, emergency room visit) or hospitalization occurs.
- Remind the participant to contact the site staff or investigator immediately if the
 participant experiences acute chest pain, shortness of breath, or palpitations
 (see Section 10.11.8.8.10).

- Schedule an appointment for the participant to return for the next study visit.
- Complete the source documents.
- The investigator or an authorized designee completes the CRFs.

10.11.8.8.4. Visit 3 – 1-Week Follow-Up Visit (After Vaccination) – 6 to 8 Days After Visit 1 for Substudy A

- Record AEs as described in Section 8.4.1.
- Record nonstudy vaccinations as described in Section 10.11.6.7.
- Record prohibited medication use as described in Section 10.11.6.7.1.
- Verify understanding of and compliance with protocol requirements for contraception as described in Section 5.3.1.
- Review laboratory results (troponin I) and ECG results. Any abnormal troponin I level
 must result in further assessments as outlined in Section 10.11.8.8.10.
- Perform 12-lead triplicate ECG. Any new ECG abnormality (compared to baseline) consistent with probable or possible myocarditis or pericarditis (as listed in Section 10.11.8.4.1) must result in further assessments as outlined in Section 10.11.8.8.10.
- Measure vital signs, including oral temperature, pulse rate, and seated blood pressure.

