- Collect a blood sample of approximately 2.5 mL as detailed in the laboratory manual for troponin I laboratory testing as described in Section 8.3.4.
- Collect a blood sample of approximately 50 mL for immunogenicity testing.
- Review the participant's reactogenicity e-diary data. If the e-diary collection period is complete:
 - Collect stop dates of any reactogenicity e-diary events ongoing on the last day that the reactogenicity e-diary was completed and record stop dates in the CRF if required.
 - Collect the participant's e-diary or assist the participant with removing the study application from his or her own personal device (if the visit is conducted after Day 7).

- Remind the participant to contact the site staff or investigator immediately if he or she
 experiences any of the following from Day 1 through Day 7 after vaccination
 (where Day 1 is the day of vaccination) to determine if an unscheduled reactogenicity
 visit is required:
 - Fever ≥39.0°C (≥102.1°F).
 - Redness or swelling at the injection site measuring greater than 10 cm (>20 measuring device units).
 - Severe pain at the injection site.
 - Any severe systemic event.
- Remind the participant to contact the site staff or investigator if a medically attended event (eg, doctor's visit, emergency room visit) or hospitalization occurs.
- Remind the participant to contact the site staff or investigator immediately if the
 participant experiences acute chest pain, shortness of breath, or palpitations
 (see Section 10.11.8.8.10).
- Schedule an appointment for the participant to return for the next study visit.
- Complete the source documents.
- The investigator or an authorized designee completes the CRFs.

10.11.8.8.5. Visit 4 – 4-Week Follow-Up Visit (After Vaccination) – 26 to 30 Days After Visit 1 for Substudy A

- Record AEs as described in Section 8.4.1.
- Record nonstudy vaccinations as described in Section 10.11.6.7.
- Record prohibited medication use as described in Section 10.11.6.7.1.
- Verify understanding of and compliance with protocol requirements for contraception as described in Section 5.3.1.
- Review laboratory results (troponin I) and ECG results. Any abnormal troponin I level
 must result in further assessments as outlined in Section 10.11.8.8.10.
- Collect a blood sample of approximately 50 mL for immunogenicity testing.

- Review the participant's reactogenicity e-diary data. Collect stop dates of any

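### The Substudy A SAP times the variant-of-concern analysis at weeks 1, 2 and 4; no week-2 sample is drawn, and the week-8 sample that is drawn is left off the list.

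*SAP*

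**What the plan says.** In the Substudy A SAP, section 6.3.1.1 (main analysis for emerging VOCs) reads "Analysis timing: 1, 2, and 4 Weeks after study intervention administration". Its reporting bullets promise VOC GMTs without naming any time points, and VOC GMFRs to every time point after vaccination. The estimand in SAP 2.2.3 defines the VOC fold rise in the same open way.

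For the secondary immunogenicity endpoints, SAP 6.2.1.1 reads "Analysis timing: 1, 4, and 8 Weeks after study intervention administration". The SAP objectives table (2.2) and the secondary estimands (2.2.2) also use weeks 1, 4 and 8.

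Protocol 10.11.4.1 says blood is "collected for immunogenicity assessments prior to Vaccination 1 and at 1, 4, and 8 weeks after vaccination". Protocol 10.11.8.1, which covers the VOC assays along with the others, says "Samples will be collected at time points as specified in Section 10.11.1 from all participants". The schedule in 10.11.1 places immunogenicity draws at Visits 1, 3, 4 and 5. For the VOC analysis itself, protocol 10.11.9.3.4 leaves the GMT time points unlisted and makes fold rises and seroresponse optional.

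**The concern.** The timing line in 6.3.1.1 is the only place in that section that enumerates time points, so it is what a programmer would use for the VOC GMT tables. It asks for a week that is not sampled and leaves out the latest immunogenicity sample in the substudy; after week 8 there is only a telephone contact at 6 months.

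What is at stake is whether VOC titers can be set beside the reference-strain and BA.4/BA.5 titers at the same weeks. If the line is followed, the GMT comparison is possible at weeks 1 and 4 but not at week 8.

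**Working it through.** **1. Is there any week-2 visit?** Week 2 is day 14 after vaccination. The protocol's visit headings (10.11.8.8.3 to 10.11.8.8.6) give:

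- Visit 2: "2 to 4 Days After Visit 1 for Substudy A". Troponin sample only, no immunogenicity draw. The number 2 here is a visit number, not a week.
- Visit 3 (week 1): "6 to 8 Days After Visit 1 for Substudy A". Immunogenicity draw of about 50 mL.
- Visit 4 (week 4): "26 to 30 Days After Visit 1 for Substudy A". Immunogenicity draw of about 50 mL.
- Visit 5 (week 8): 52 to 60 days after Visit 1. Immunogenicity draw of about 50 mL.

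No visit is scheduled between day 8 and day 26.

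**2. Does the stated blood volume allow an extra draw?** Protocol 10.11.8 gives a minimum of about 210 mL per participant.

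- Immunogenicity: 4 draws (baseline, weeks 1, 4, 8) x 50 mL = 200 mL.
- Troponin: 4 draws (screening, Visits 1, 2, 3) x 2.5 mL = 10 mL.
- Total: 200 + 10 = 210 mL, which reproduces the protocol's figure.
- With a week-2 draw added: 5 x 50 + 10 = 260 mL, which does not.

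So there is no unlisted week-2 immunogenicity sample.

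**3. Compare the two sets of weeks.**

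- VOC timing line {1, 2, 4} less sampled weeks {1, 4, 8} = {2}: listed but not sampled.
- Sampled weeks {1, 4, 8} less VOC timing line {1, 2, 4} = {8}: sampled but not listed.

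**4. Compare within the section.** For GMTs, only the timing line sets the weeks, so week 8 falls out. For GMFRs, the timing line excludes week 8 while the reporting bullet and the estimand include it, so the SAP gives two answers.

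**5. Size.** SAP Table 2 shows BNT162b2 in Groups 1, 2, 3 and 6. With 30 per group in each of 2 age strata, 4 x 30 x 2 = 240 planned participants. SAP 2.3 allows dose-level combinations 1 and/or 3 to be omitted:

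- one omitted: 3 x 30 x 2 = 180
- both omitted: 2 x 30 x 2 = 120
- VOC assays not run: 0

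The analysis set is the evaluable immunogenicity population, so any realised number cannot exceed these planned figures if enrollment is as planned.

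**The case against.** The best case for leaving the line alone is that little follows from it. The endpoint is exploratory, Substudy A has no hypotheses, and protocol 10.11.8.1 makes assays for other VOCs optional. Protocol 10.11.4.1 also lets the sponsor stop collecting or not analyse a group's samples. Amendment 6 moved weeks 1 and 8 to exploratory status even for the matched strains, so the misalignment does not touch the 4-week results. All of this stands, and it limits the weight of the point.

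A second argument is that protocol 10.11.9.3.4 does not commit to week-8 VOC GMTs, so weeks 1 and 4 alone would comply. That also stands, and the fix allows for it. It does not explain week 2. Nor does the clause in SAP 2.1 letting the SAP modify the protocol: no visit collects the sample. The mismatch is also not the product of reading an older SAP against a later amendment, because the same SAP uses weeks 1, 4 and 8 elsewhere.

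Two stronger readings are tempting and not supported:

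- A reader might infer that week 8 is removed from the VOC analysis altogether. The fold-rise bullet in 6.3.1.1 and the estimand in 2.2.3 cover every postvaccination time point, and the VOC comparisons in 6.3.2 carry no timing restriction. For fold rises the SAP is contradictory; it does not cleanly exclude week 8.
- A reader might infer that a nonexistent visit would yield wrong estimates. With no week-2 sample the result is an empty column or a programming query, not a biased figure.

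**Conclusion.** The timing line is wrong as written. It lists an unsampled week 2, omits the sampled week 8, and conflicts with the draw schedule, with SAP 6.2.1.1 and with the fold-rise wording in its own section. Taken literally, week-2 output is empty, week-8 VOC GMTs are not reported, and GMFR timing is undetermined.

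The size is a ceiling of about 240 planned participants, assuming all four BNT162b2-containing groups enroll in full in both strata and the VOC assays are run; it is not an expected loss. No primary or secondary result, hypothesis test, error rate or sample-size basis is affected. This is worth correcting because it is an operative instruction to programmers and the correction is trivial.

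**What to change.** In section 6.3.1.1 of the Substudy A SAP, change the analysis timing to weeks 1, 4 and 8. That matches 6.2.1.1, the draw schedule and the section's own fold-rise bullet. If fewer VOC time points are intended, list only weeks that are sampled, and narrow the fold-rise wording in 6.3.1.1 and 2.2.3 to the same list.

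The cost is one line of SAP text, or a few if the shorter list is chosen. No new visit, sample or blood volume is needed.
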